8.4. Safety Analyses

All subjects with at least 1 dose of study medication will be included in the safety analyses. Baseline assessments are done at Day 1 (Visit 3). If Visit 3 data is missing the last available observation prior to start of study treatment is considered as a baseline.

No inferential safety analyses are planned. Pfizer safety reporting standards will be utilized for all safety endpoints.

All safety analyses will be presented overall, and separately by age group of pediatrics overall (<17 years) and adults (17-65 years).

8.4.1. Adverse Events

All AEs occurring during the course of the study will be coded using MedDRA coding dictionary.

All AEs (serious and non-serious) reported from the first day of study treatment through and including 28 calendar days after the last administration of the study drug will be considered treatment emergent AEs (TEAEs). An overall summary of treatment-emergent AEs will be provided. TEAEs will also be summarized by system organ class, preferred term, severity, and relationship to study drug. TEAEs will be presented overall, and separately by age group of pediatrics overall (<17 years) and adults (17-65 years).

Summaries and listings of all AEs, SAEs and treatment-related AEs will be presented in accordance with the current Pfizer Standard Operating Procedures (SOPs) and standards.

The 3-tier Approach for summarizing AEs will be implemented, and events (MedDRA PTs) will be classified into the following tier definitions:

Tier 1: None

Tier 2: Targeted Medical Events (TMEs) identified in the Lyrica Safety Review Plan

Tier 3: Standard safety output (no new outputs-see above)

The Tier 2 and 3 AEs will be presented overall, and separately by age group of pediatrics overall (<17 years) and adults (17-65 years).

8.4.2. Suicidal Ideation and Behavior

C-CASA/C-SSRS

The denominator used in the percentages will be the number of subjects assessed for suicidal ideation and behavior. For worsening, the denominator would include the subset of subjects who had any level of suicidal ideation and behavior reported at baseline. For new onset, the denominator would include the subset of subjects with no suicidal ideation and behavior reported at baseline.

A subject listing of C-CASA categories as well as the underlying C-SSRS scale data will be presented.

In addition, a summary table with the number and percent of subjects within each C-CASA category by treatment group at screening, baseline, and at any time post-baseline without regard to baseline will be reported.

C-CASA will be presented overall, and separately by age group of pediatrics overall (<17 years) and adults (17-65 years).

8.5. Summary of Efficacy Analyses

Endpoint (Key Summary Metrics)	Analysis Set	Statistical Method	Model/ Covariates/ Strata	Missing Data	Interpretation
Log _e 28-day PGTC seizure rate (N, LS Mean Diff/SE)	ITT	ANCOVA	Treatment, region, age strata, baseline seizure rate	Days missing from Seizure Diary will be subtracted from rate calculations	Primary Analysis Note: age strata is protocol defined age strata. Baseline is the log of 28-day PGTC rate at baseline
Key summary statistics will be presented for the Log _e 28-day PGTC seizure rate and for the back transformed “percent reduction in seizures” relative to placebo.					
Log _e 28-day PGTC seizure rate (N, LS Mean Diff/SE) (treatment-by-age p-value)	ITT	ANCOVA	Treatment, region, age group, treatment-by-age group interaction, baseline seizure rate	Days missing from Seizure Diary will be subtracted from rate calculations	Supplemental Analysis Note: age groups are Age < 17 yrs and Age ≥ 17 yrs. Baseline is the log of 28-day PGTC rate at baseline.
Key summary statistics will be presented for the Log _e 28-day PGTC seizure rate and for the back transformed “percent reduction in seizures” relative to placebo.					
Responder rate (%)	ITT	Logistic regression	Treatment, region, age strata	Days missing from Seizure Diary will be subtracted from rate calculations	Secondary Analysis
Proportion Seizure-free days (%)	ITT	ANCOVA	Treatment, region, age strata, baseline	Days missing from Seizure Diary will be subtracted from rate calculations	Exploratory Analysis Each seizure type: PGTC, myoclonic, tonic/tonic, absence, and clonic seizures. Baseline for this endpoint is the proportion of seizure free days at baseline.
Number of seizure-free days gained (N, Mean, SE)	ITT	ANCOVA	Treatment, region, age strata, baseline	Days missing from Seizure Diary will be subtracted from rate calculations	Exploratory Analysis Each seizure type: PGTC, myoclonic, tonic/tonic, absence, and clonic seizures. Baseline for this endpoint is the number of adjusted seizure free days at baseline.

Proportion PGTC Seizure-freedom (%)	ITT	Logistic regression	Treatment, region, age strata	Days missing from Seizure Diary will be subtracted from rate calculations	Exploratory Analysis
Log _e 28-day PGTC seizure rate (N, LS Mean Diff/SE)	ITT	ANCOVA	Treatment, region, age strata, baseline	Multiple imputation will be applied.	Sensitivity Analysis. Baseline is the log of 28-day PGTC rate at baseline.
Log _e 28-day PGTC seizure rate (N, LS Mean Diff/SE)	ITT	ANCOVA	Treatment, region, 2 age groups , baseline	Days missing from Seizure Diary will be subtracted from rate calculations	Sensitivity Analysis Note: age group are Age< 17 yrs and Age>= 17 yrs. Baseline is the log of 28-day PGTC rate at baseline
Log _e 28-day PGTC seizure rate (N, LS Mean Diff/SE)	ITT	ANCOVA	Treatment, pooled region, 2 age groups , baseline	Days missing from Seizure Diary will be subtracted from rate calculations	Sensitivity Analysis Note: age group are Age< 17 yrs and Age>= 17 yrs. US and European Union will be pooled in the region class. Baseline is the log of 28-day PGTC rate at baseline
Change from baseline to double blind phase of Log _e 28-day PGTC seizure rate	ITT	Rank ANCOVA	Treatment, region, age strata, region and ranked log-BL		Sensitivity Analysis (Log-Scale). Baseline is the ranked log of 28-day PGTC rate at baseline.
Change from baseline to double blind phase of Log _e 28-day PGTC seizure rate (DB Phase)	ITT	Wilcoxon-Mann Whitney Test			Sensitivity Analysis (Log-Scale)
Raw Seizure Count	ITT	GENMOD, Poisson and negative binomial distribution with log link	Treatment, and baseline		scale parameter = Pearson for the Poisson model. Baseline for this endpoint is seizure count at baseline.

- All efficacy endpoints will be presented descriptively overall, and separately as by age group of pediatrics overall (<17 years) and adults (17-65 years).

Appendix 1. Data Derivation Details

This table describes how seizure related endpoints have been defined.

Endpoint	Derivation
8-week baseline phase (b) 28-day seizure rate	28-day seizure rate _b = [(# of seizures _b) ÷ (#of days _b - # of missing diary _b)] × 28, where #of days _b is defined as (first dose date-1) – screening date +1.
12-week double-blind treatment phase (t) 28-day seizure rate	28-day seizure rate _t = [(# of seizures _t) ÷ (#of days _t - # of missing diary _t)] × 28, where #of days _t is defined as date of last dose in phase – date of first dose in phase +1.
Primary endpoint : Log _e of 28-day seizure rate during 12-week double-blind treatment phase	Log _e (28-day seizure rate _t +1)
“Percent reduction in seizures” relative to placebo	
For example, a difference between one of the pregabalin doses and placebo of -0.400 on the log transformed scale for the 28-day seizure rate translates into a 33% reduction in the 28-day seizure rate of the pregabalin group from the placebo group (ie, 100%*[exp-0.400-1] = -33%)
 
An additional back transformation will be calculated for the percent reduction in seizures for each pregabalin treatment group relative to placebo for presentation in the CSR as follows:
 $100\% \times \frac{\exp(\text{LSMean(pregabalin)}) - 1 - [\exp(\text{LSMean(placebo)}) - 1]}{\exp(\text{LSMean(placebo)}) - 1}$
Percent change from baseline in 12-week 28-day seizure rate	% Change = [28-day seizure rate _t - 28-day seizure rate _b] / 28-day seizure rate _b] × 100%
Responders	
≥50% reduction in the 28-day seizure rate from baseline during the 12-week double-blind treatment phase, then response = 1 (responder) otherwise response = 0 (non-responder).
 
The response status will be set as missing if the baseline seizure rate is missing. If baseline seizure rate is non-missing but there are no double-blind phase seizure rates, then the response status will be set as non-response

Proportion Seizure-free days	The numerator for seizure-free days is defined as the number of days the subject experience no seizures over the double-blind assessment phase.

Number of seizure-free days gained	The number of seizure-free days will be adjusted to a per 12 weeks value (ie, 84 days) for the baseline and 12-week double-blind assessment phases. Changes from baseline are to be computed and the analysis performed accordingly. Number of 12 week adjusted seizure free days is defined as follows: Number of seizure free days in a period x 84 / number of days in a period.
Proportion PGTC Seizure-freedom	The numerator for seizure-freedom is defined as the number of subjects that experience no PGTC seizures over the last 28 days of the double-blind assessment phase (Patient must have received at least 42 days (2 weeks + 28 days) of study medication and have a minimum of 21 of the last 28 days as non-missing diary). The denominator is the ITT population with 42 days (2 weeks + 28 days) of study medication.

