5. ANALYSIS SETS

5.1. Full Analysis Set (Intent-to-Treat Population)

The efficacy analyses will be performed on the intent to treat (ITT) population which consists of randomized subjects who took at least 1 dose of investigational product during the double-blind assessment phase, have a baseline value and at least 1 post-baseline efficacy assessment (diary entry).

5.2. 'Per Protocol' Analysis Set (PP Population)

None. Protocol Deviations will be addressed (See [Section 5.6](#)) but no PP analyses are planned.

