6.1.2. Secondary Efficacy Endpoint

Responder Rate, defined as subjects who have a $\geq 50\%$ reduction in the 28-day seizure rate for all PGTC seizures during the double-blind assessment phase, as measured from baseline (data collected during the 8-week baseline phase) will be defined as a responder, otherwise they be considered as a non-responder.

The responder rate will be based on the percentage change from baseline in the 12-week double-blind treatment phase 28-day seizure rate, which is defined as follows:

$\% \text{ Change} = [(28\text{-day seizure rate}_t - 28\text{-day seizure rate}_b) / 28\text{-day seizure rate}_b] \times 100\%$, where t is the 12-week double-blind treatment phase and b is for the 8-week baseline phase.

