7. HANDLING OF MISSING VALUES

Missing data will be handled based on the nature of the endpoint and the proposed statistical methods for analyzing the data.

For all endpoints that include seizure rate, days with missing seizure diary data will be subtracted from the seizure rate calculations. If seizure rate for any phase cannot be calculated for a subject due to missing information, the endpoint that involves seizure rate during that phase will be also missing for that subject.

For scales used in this study, scores will be imputed according to the imputation rules and algorithms for missing component scores that are provided in the data standard documents. Partial dates for AEs and concomitant medications will be imputed according to Pfizer standard algorithms.

The assessment of missing data for the primary endpoint will require the construction of the following windows and drop-out categories:

- *Windowing for each subject will be constructed for the 1st month, 2nd month, and 3rd month the subject was in the study. Thus a 28-day seizure rate will be determined for each windowed month for which seizure data exist, otherwise the seizure data will be considered missing with a corresponding reason for it being missing. Specific details are provided in [Appendix 3](#).*
- *Drop-out patterns will be constructed based on the reason the seizure data is missing for the corresponding windowed month. Hence, the following drop-out patterns will be defined for three specific categories of related to lack of efficacy or adverse event or other reason:*
 - *Completed study as planned.*
 - *Drop-out due to lack of efficacy:*
 - *Drop-out at month 1 due to lack of efficacy;*
 - *Drop-out at month 2 due lack of efficacy;*
 - *Drop-out at month 3 due to lack of efficacy.*
 - *Drop-out due to an adverse event:*
 - *Drop-out at month 1 due to an adverse event;*
 - *Drop-out at month 2 due to an adverse event;*
 - *Drop-out at month 3 due to an adverse event.*
 - *Drop-out due to other reason:*
 - *Drop-out at month 1 due to other reason;*
 - *Drop-out at month 2 due to other reason;*
 - *Drop-out at month 3 due to other reason.*

Other reason includes any drop-outs excluding efficacy and adverse event.

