Appendix 2. C-SSRS Mapped to C-CASA - Suicidal Ideation and Behavior Events and Codes

C-CASA Event Code	C-CASA Event	C-SSRS Response
1	Completed suicide	As captured in the safety database
2	Suicide attempt	“Yes” on “Actual Attempt”
3	Preparatory acts towards imminent suicidal behavior	“Yes” on any of the following: 
 • “Aborted attempt”, or • “Interrupted attempt”, or • “Preparatory Acts or Behavior”
4	Suicidal ideation	“Yes” on any of the following: 
 • “Wish to be dead”, or • “Non-Specific Active Suicidal Thoughts”, or • “Active Suicidal Ideation with Any Methods (Not Plan) without Intent to Act”, or • “Active Suicidal Ideation with Some Intent to Act, without Specific Plan”, or • “Active Suicidal Ideation with Specific Plan and Intent”
7	Self-injurious behavior, no suicidal intent	“Yes” on “Has subject engaged in Non-suicidal Self-Injurious Behavior?”

Appendix 3. Windowing for Study Months 1, 2 and 3

A 28-day seizure rate will be determined for each windowed month for which seizure data exist. Assignment of seizure data to visits during the Double-Blind Treatment Phase will use visit windows based on the day of the assessment relative to the date of the start of the double blind treatment phase. The following visit windows will be defined for statistical outputs:

Visit Windows

Month	Time Interval (Days)
Month 1	1 to 28
Month 2	29 to 56
Month 3	57 to 90

Derive study day as the (assessment date-date of start of double blind treatment phase) + 1. A subject must have at least 24 diary days to be counted in any monthly visit window data. Any data collected after Day 90 will be excluded from the monthly visit window calculations.

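### The responder rule sets no minimum follow-up, so a subject who stops after a few seizure-free days counts as a 12-week responder, and the planned non-response rule reaches almost nobody

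*SAP*

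**What the plan says.** - **Rate.** The double-blind 28-day rate is seizures divided by evaluable days, times 28 (SAP Section 6.1.1 and Appendix 1), "where #of days _t is defined as date of last dose in phase – date of first dose in phase +1". Under Section 7, "days with missing seizure diary data will be subtracted from the seizure rate calculations". No minimum number of days is set.
- **Response.** Appendix 1 assigns response when there is "≥50% reduction in the 28-day seizure rate from baseline during the 12-week double-blind treatment phase, then response = 1 (responder". Section 6.1.2 adds for everyone else: "otherwise they be considered as a non-responder".
- **No double-blind rate.** Appendix 1: "If baseline seizure rate is non-missing but there are no double-blind phase seizure rates, then the response status will be set as non-response". Section 7, for a phase whose rate cannot be calculated: "the endpoint that involves seizure rate during that phase will be also missing for that subject".
- **Population.** Section 8.2 analyses responders in the ITT set. Section 5.1 limits that set to randomized, dosed subjects who "have a baseline value and at least 1 post-baseline efficacy assessment (diary entry".
- **Minimum-data rules elsewhere.** Seizure-freedom requires 42 or 84 days of medication plus diary completeness (Section 6.1.3.3). Monthly rates carry a threshold in Appendix 3: "A subject must have at least 24 diary days to be counted in any monthly visit window data".
- **Drop-out analyses.** Multiple imputation is planned for the primary endpoint (Section 8.1), and the Appendix 4 code fills in only missing rates. Sections 8.2 and 8.5 plan no responder analysis that addresses drop-out.

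**The concern.** The responder rate is the only secondary efficacy endpoint and carries the secondary objective. A subject who stops on day 5 without a PGTC seizure has a rate of 0, a 100% reduction, and is reported as a responder over 12 weeks. Over a short period, a halving of the rate is likely by chance alone. The rule that looks like protection against this covers a group that the ITT definition has already nearly emptied. If one arm loses more subjects early for reasons unrelated to seizures, such as adverse events, its responder rate rises without any drug effect. Neither the analysis nor a planned sensitivity analysis would show by how much.

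**Working it through.** **The plan's own figure.** The SAP states no responder rate or responder power. Its design figure, power 0.800 for Dose Level 1 with 56 per group, difference 0.358 and SD 0.67, reproduces (0.800 by noncentral t). It concerns the primary endpoint and is not in dispute.

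**Who is left for the non-response rule.** An ITT member has a dose, a baseline value and a post-baseline diary entry. The double-blind rate exists as soon as one dosed day has a diary entry. Only rare cases remain, such as a sole entry that falls outside the phase. For these, Appendix 1 gives non-response and Section 7 gives missing.

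**Chance of response with no drug effect.** From the SAP: 56-day baseline, 84-day double-blind phase, 50% threshold. Assumed: Poisson counts at the same rate λ per 28 days before and after randomization, at least one baseline seizure, and drop-out unrelated to seizures.

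With baseline count b ~ Poisson(2λ) and d evaluable double-blind days, y ~ Poisson(λd/28). The subject responds if (y/d) × 28 ≤ 0.5 × (b/56) × 28, that is, if y ≤ bd/112.

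Example, λ = 2, d = 7: y must be at most b/16, so y = 0 whenever b ≤ 15, and the chance is exp(-0.5) = 0.607. At d = 84, y ~ Poisson(6) must be at most 0.75b. Summing over b gives 0.160.

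| Evaluable days | λ = 2 | λ = 3 |
|---|---|---|
| 7 | 60.7% | 47.3% |
| 10 | 49.0% | 35.0% |
| 14 | 38.7% | 30.9% |
| 28 | 31% | 24% |
| 84 | 16.0% | 10.4% |

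With gamma variation between subjects (variance 0 to 1.0) and baseline means of 1.5 to 6, the ranges are 28-69% at day 7 and 3-24% at day 84.

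**Effect on the comparison.** Suppose a share a of one arm and a share p of the other stop at day 10 and the rest complete. The spurious difference is (a - p) × (P10 - P84), where P10 and P84 are the table values. All shares are assumed.

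- 15% against 5%: λ = 2 gives 0.10 × (0.490 - 0.160) = +3.3 points; λ = 3 gives 0.10 × (0.350 - 0.104) = +2.5 points.
- 10% against 5%: +1.7 and +1.2 points.
- 7% against 5%: +0.7 and +0.5 points.

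If those drop-outs count as non-responders, the 15% against 5% case gives -(a - p) × P84: -0.10 × 0.160 = -1.6 points and -0.10 × 0.104 = -1.0 point.

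With between-subject variance 0.5, baseline means of 2 to 4, drop-out at day 7 or 14, and 5% against 10-20% stopping, the present rule gives +1.1 to +6.4 points and non-response gives -0.5 to -2.9.

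**With a drug effect.** Take the SAP's 41.4% reduction as a rate ratio of 0.586 (an approximation, since the SAP states it on the log(rate + 1) scale), with the same 15% against 5% at day 10.

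| | All complete | Present rule | Drop-outs as non-responders |
|---|---|---|---|
| λ = 2 | 29.4 | 30.9 (+1.4) | 23.4 (-6.0) |
| λ = 3 | 31.6 | 32.1 (+0.6) | 25.8 (-5.8) |

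Entries are differences in points; shifts from full completion, taken before rounding, are in brackets.

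**The case against.** **Direction.** A reader might infer that the rule always favours the arm with more early discontinuation, or that it favours pregabalin. The SAP supports neither. It gives no drop-out rates and does not say which arm will lose more subjects. The discontinuation events listed in Section 3.1 are seizure-related, and subjects who leave because PGTC seizures increase will mostly be non-responders already. The shift comes only from early drop-out unrelated to seizures. This limit stands. In the example with a baseline mean of 3 and variance 0.5, however, the shift disappears only if about 86% of early drop-outs are non-responders (1 - 0.142).

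**Size.** Having 15% against 5% stop by day 10 puts every drop-out inside the two-week escalation. With 56 per arm, the standard error of a difference near 16% is √(2 × 0.16 × 0.84 / 56) = 6.9 points. So 3.3 points is about half a standard error, or fewer than two subjects (0.033 × 56 = 1.8). This also stands.

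**Remedy.** A reader might infer that every discontinuation for adverse event, death or insufficient response must become a non-response in the main analysis. That would answer a different question, because it also reclassifies someone who stops near the end with almost full data. At the design effect it moves the estimate further from the full-completion value than the present rule does. It is a legitimate estimand, but not the correction of an error. Version 4.0 also revised the definition to match the adult study, so changing the main rule has a consistency cost.

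**Another reading.** The plural in Appendix 1 could mean the monthly rates, which need 24 diary days. Appendix 3 confines that threshold to the monthly windows, and Appendix 1 defines the phase rate without it, so this reading is weak. If it was intended, the SAP should say so.

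**Conclusion.** The point holds in a limited form. On the SAP's text it is certain that response has no minimum follow-up, that the non-response rule is close to empty within the ITT set, that Section 7 and Appendix 1 disagree on the few subjects it covers, and that no responder analysis addresses drop-out. The bias is conditional on early drop-out that is unrelated to seizures and unequal between arms. The size rests on assumed seizure rates, Poisson or gamma-Poisson counts, and assumed drop-out shares and timing. Responder p-values are nominal (Section 8.2) and the decision rules concern the primary endpoint only (Section 4.2), so the primary conclusion does not change. The planned drop-out tables by month, reason and arm (Section 7) would reveal an imbalance but not its effect on the responder rate. A pre-specified sensitivity analysis should be added; the SAP does not show that the main definition must be replaced.

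**What to change.** Before unblinding, amend Section 8.2, Appendix 1 and the Section 8.5 table:

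1. Pre-specify a responder analysis in which subjects with fewer than 24 evaluable double-blind diary days are non-responders, at least as a sensitivity analysis beside the present rule. The threshold is the SAP's own. It reduces the problem without removing it: at 28 days the no-effect chance of response is still 24-31%.
2. Add a second sensitivity analysis in which discontinuations for adverse event, death or insufficient clinical response (Impstat = 1 in Appendix 4) are non-responders, labelled as a different estimand.
3. Reconcile Section 7 and Appendix 1 on whether a subject with no double-blind rate is missing or a non-responder, and state that the rate meant is the phase rate.

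The cost is SAP wording and one or two tables. Both analyses shift the result against the arm with more drop-out. If the main rule itself is changed, the definition no longer matches the adult study's.
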